10.2 Key Efficacy Variables

The following key efficacy variables will be summarized at all visits for each population:

- Proportion of subjects achieving $\geq 90\%$ reduction in Psoriasis Area and Severity Index (PASI) score (PASI 90)
- Proportion of subjects achieving the Static Physician Global Assessment (sPGA) score of clear or almost clear
- Proportion of subjects achieving $\geq 75\%$ reduction in PASI score (PASI 75)
- Proportion of subjects achieving 100% reduction in PASI score (PASI 100)
- Proportion of subjects achieving the sPGA score of clear

10.3 Additional Efficacy Analyses

The following additional efficacy variables will be summarized at all visits for each population:

- Proportion of subjects achieving $\geq 50\%$ reduction in PASI score (PASI 50)
- Proportion of subjects achieving absolute PASI of < 3
- Proportion of subjects achieving DLQI score of 0
- Proportion of subjects achieving DLQI score of 0 or 1
- Proportion of subjects achieving a reduction of at least 5 points in DLQI, among subjects with baseline value ≥ 5
- Change and percent change from baseline in PASI
- Change and percent change from baseline in DLQI
- Change and percent change from baseline in NAPSI, among subjects with baseline value > 0
- Change and percent change from baseline in PPASI, among subjects with baseline value > 0
- Change and percent change from baseline in PSSI, among subjects with baseline value > 0

10.4 Efficacy Variables for Interim Analysis

All key efficacy and additional efficacy variables listed in Section 10.2 and Section 10.3 will be performed for the interim analysis for each population except for ALL_RZB

Population. All endpoints will be analyzed up to the last visit with at least one subject has observed measurements of that variable, by the time of the interim data cutoff.

10.5 Efficacy Subgroup Analysis

For RZB, RZB_NL, Retreatment and UST_RZB Populations, key efficacy variables will be summarized in the subgroup including subjects from Japan only. This subgroup analysis will only be performed in the final analysis, upon study completion.

In addition, PASI 90 and sPGA clear or almost clear will be summarized among the RZB Population at Week 208 and Week 256, by anti-drug antibody (ADA) and by neutralizing antibody (nAB) status by Week 208 and Week 256, respectively.

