1. Subjects with moderate to severe chronic plaque psoriasis who have completed one of the preceding Studies 1311.3, 1311.4, 1311.13, 1311.28, 1311.30, 1311.38 and M16-178.	
2. Subjects must be candidates for prolonged open label risankizumab treatment according to investigator judgment	
Main Exclusion:	
1. Premature discontinuation for any reason in the preceding study.	
Investigational Product:	Risankizumab (ABBV-066): 75 mg pre-filled syringe, 90 mg/mL, 0.83 mL dispensed volume, 0.87 mL fill volume
Dose:	Risankizumab (ABBV-066): 150 mg administered every 12 weeks
Mode of Administration:	Subcutaneous injection
Duration of Treatment: The study duration is 252 weeks.	
Criteria for Evaluation:	
Efficacy:	
Key variables to be summarized at all visits:	

• Proportion of subjects achieving $\geq 90\%$ reduction in Psoriasis Area and Severity Index (PASI) score (PASI 90)• Proportion of subjects achieving the Static Physician Global Assessment (sPGA) score of clear or almost clear• Proportion of subjects achieving $\geq 75\%$ reduction in PASI score (PASI 75)• Proportion of subjects achieving 100% reduction in PASI score (PASI 100)• Proportion of subjects achieving the sPGA score of clear	
Pharmacokinetics (PK) and Immunogenicity:	
Blood samples will be collected for measurement of risankizumab concentration and anti-drug antibody (ADA) and neutralizing antibody (NAb) just prior to dosing at Baseline, Week 48, Week 96, Week 156, Week 204 and End of Treatment (EOT) visit.	
Safety:	
Adverse events (AE)s, laboratory data and vital signs will be assessed throughout the study.	
Statistical Methods:	
Efficacy:	
For all efficacy analyses (including the assessment of PASI responses), baseline refers to the last non-missing value prior to the first dose of study drug in the preceding studies.	
Summary statistics will be provided. Continuous variables will be summarized by the number of observations, mean, standard deviation, median, minimum, maximum, 25 th and 75 th percentile, as well as the 95% confidence intervals (CIs) of mean values. Categorical variables will be summarized by counts and percentages, as well as the 95% CIs of the percentages.	

Statistical Methods (Continued):

Pharmacokinetics (PK) and Immunogenicity:

Risankizumab plasma concentrations will be determined. Descriptive statistics will be calculated for each sampling time (study visit). The number and percentage of subjects with ADA will be calculated.

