4.2 Design Diagram

This is a Phase 3, single-arm, multicenter, OLE study designed to investigate the long term safety and efficacy of risankizumab 150 mg E12W in the treatment of moderate to severe chronic plaque psoriasis. Approximately 2200 subjects who meet the entry criteria are planned to be enrolled in this study, rolling over from the preceding Studies 1311.3, 1311.4, 1311.13, 1311.28, 1311.30, 1311.38, and M16-178 (Phase 2/3, randomized clinical studies in subjects with moderate to severe chronic plaque psoriasis, conducted by Boehringer Ingelheim or AbbVie).

All subjects need to complete one of the preceding Phase 2/3 psoriasis studies. The subject preferably has the Baseline visit of Study M15-997 on the same day of the completion visit of the preceding study; however, the Baseline visit can be delayed up to 8 weeks if needed. All subjects will be administered 150 mg risankizumab s.c. at the Baseline visit, and from the Baseline visit onwards, risankizumab will be administered subcutaneously E12W during the study. Study visits for dosing, efficacy and safety assessments will be performed E12W starting from Baseline until the Week 156 visit. After this visit until the End of Treatment (EOT) visit at Week 252, study visits will be performed E24W. The schematic of the study is shown in [Figure 1](#).

Figure 1. Study Schematic

There is a ± 7 days visit window for study visits. Every effort will be made to bring subjects back to their original scheduled visit (calculated from Baseline) if they are out of the visit window. Subjects who discontinue study drug treatment early will need to attend an early EOT visit ideally within 2 weeks after the decision and preferably prior to the administration of any new therapies.

All subjects, including those that prematurely discontinued study drug treatment, will return to the clinic for an End of Observation Visit (EOO) 20 weeks after their last administered dose of risankizumab. Study completion is defined as a subject having completed the EOO visit.

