5.1 Definition for Analysis Populations

RZB Population:

The RZB population consists of subjects who were randomized to risankizumab 150 mg in Studies 1311.3, 1311.30, 1311.28, 1311.38, and M16-178. This population will be used to evaluate the long-term safety and efficacy of risankizumab 150 mg with loading dose. For subjects from Japan, data after the first dose of risankizumab 150 mg from the preceding studies, and prior to the start of 75 mg dose will be used for the analyses.

RZB_NL Population:

The RZB_NL population consists of subjects who were randomized to placebo in the initial study and switched to risankizumab 150 mg (without loading dose) in Studies 1311.3, 1311.4, 1311.28, and 1311.38. This population will be used to evaluate the long-term safety and efficacy of risankizumab 150 mg without initial loading dose. For subjects from Japan, data after the first dose of risankizumab 150 mg from the preceding studies, and prior to the start of 75 mg dose will be used for the analyses.

Retreatment Population:

The Retreatment population consists of subjects who were re-randomized to placebo in Part B of Study 1311.4 and received retreatment of risankizumab 150 mg. This population will be used to evaluate the safety and efficacy of re-treatment after temporary withdrawal. For subjects from Japan, data after the re-treatment and prior to the start of 75 mg dose will be used for the analyses.

UST_RZB Population:

The UST_RZB population consists of subjects who were randomized to ustekinumab in Studies 1311.3 and 1311.28. This population will be used to assess the safety and efficacy of risankizumab 150 mg when subjects switch from ustekinumab to risankizumab

150 mg. For subjects from Japan, data prior to the start of 75 mg dose will be used for the analyses.

ADA RZB Population:

The ADA_RZB population consists of subjects who were randomized to adalimumab in Study 1311.30 and switched to risankizumab. This population will be used to assess the safety and efficacy of risankizumab when subjects from adalimumab to risankizumab.

FUM RZB Population:

The FUM_RZB Population consists of subjects who were randomized to Fumaderm[®] (fumaric acid esters) in Study M16-178. This population will be used to assess the safety and efficacy of risankizumab when subjects switch from Fumaderm[®] to risankizumab.

RZB Japan Population:

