For efficacy analyses, local tolerability, laboratory parameters, and vital sign variables, analysis windows are constructed using the following algorithm:

- Determine the nominal Rx day for each visit (e.g., Week 4 [4 weeks after Baseline visit] equals Rx Day 29).
- In order to include all post baseline data, the first post-baseline interval starts on the first day after the first dose of risankizumab (Rx Day 2).
- Determine the window around a specific nominal Rx day by adding or subtracting half of the interval between adjacent visits (e.g., days between Week 2 and Week 4 is 14). The threshold between adjacent visits is determined by splitting the interval evenly between the visits. If the resulting split is between Rx days, then the threshold is determined as the midpoint between the adjacent visits. If the resulting split is on an Rx day, then the threshold is determined as being between that Rx day and the Rx day prior to it (e.g., the split between Week 2 and Week 4 would be between Rx Days 22 and 23).
- If more than one assessment is included in a time window the assessment closest to the nominal day will be used. If there are two observations

equidistant to the nominal day, the one after the nominal day will be used in analyses. If more than one post baseline assessment is included on the same day, then the worst assessment on that day will be used in analyses, except those specified in Section 11.0.

The protocol specified visits and corresponding time windows used in the efficacy analyses, local tolerability, laboratory parameters, and vital sign variables, are presented in the following tables.

Table 1. Visit Windows for Analysis of PASI, sPGA, Local Tolerability Assessment, Clinical Laboratory Tests, and Vital Signs (RZB Population)

Window Label	Target Day	Interval
Baseline ^a	1	≤ 1 ^b
Week 4	29	[2, 43]
Week 8	57	[44, 71]
Week 12	85	[72, 99]
Week 16	113	[100, 155]
Week 28	197	[156, 239]
Week 40	281	[240, 323]
Week 52	365	[324, 407]
Week 64	449	[408, 491]
Week 76	533	[492, 575]
Week 88	617	[576, 659]
Week 100	701	[660, 743]
Week 112	785	[744, 827]
Week 124	869	[828, 911]
Week 136	953	[912, 995]
Week 148	1037	[996, 1079]
Week 160	1121	[1080, 1163]
Week 172	1205	[1164, 1247]
Week 184	1289	[1248, 1331]
Week 196	1373	[1332, 1415]
Week 208	1457	[1416, 1541]
Week 232	1625	[1542, 1709]
Week 256	1793	[1710, 1877]
Week 280	1961	[1878, 2045]
Week 304	2129	[2046, 2199]

a. There is no baseline for local tolerability measurements.

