b. If time is collected in vital signs, restrict to records prior to the first dose of study drug.

Note: Rx Day calculated relative to first dose date of risankizumab.

Table 2. Visit Windows for Analysis of Efficacy Variables (DLQI/NAPSI/PSSI/PPASI) (RZB Population)

Window Label	Target Day	Interval
Baseline	1	≤ 1
Week 16	113	[2, 239]
Week 52	365	[240, 449]
Week 76	533	[450, 617]
Week 100	701	[618, 785]
Week 124	869	[786, 953]
Week 148	1037	[954, 1121]
Week 172	1205	[1122, 1289]
Week 196	1373	[1290, 1415]
Week 208	1457	[1416, 1541]
Week 232	1625	[1542, 1709]
Week 256	1793	[1710, 1877]
Week 280	1961	[1878, 2045]
Week 304	2129	[2046, 2199]

Note: Rx Day calculated relative to first dose date of risankizumab.

Table 3. Visit Windows for Analysis of PASI, sPGA, Local Tolerability Assessment, Clinical Laboratory Tests, and Vital Signs (RZB_NL Population)

Window Label	Target Day	Interval
Switch to RZB	1	$\leq 1^a$
Week 12S	85	[2, 127]
Week 24S	169	[128, 211]
Week 36S	253	[212, 295]
Week 48S	337	[296, 379]
Week 60S	421	[380, 463]
Week 72S	505	[464, 547]
Week 84S	589	[548, 631]
Week 96S	673	[632, 715]
Week 108S	757	[716, 799]
Week 120S	841	[800, 883]
Week 132S	925	[884, 967]
Week 144S	1009	[968, 1051]
Week 156S	1093	[1052, 1135]
Week 168S	1177	[1136, 1219]
Week 180S	1261	[1220, 1303]
Week 192S	1345	[1304, 1429]
Week 216S	1513	[1430, 1597]
Week 240S	1681	[1598, 1765]
Week 264S	1849	[1766, 1933]
Week 288S	2017	[1934, 2087]

S = Switch to Risankizumab

a. If time is collected in vital signs, restrict to records prior to the first dose after switch to RZB.

Note: Rx Day calculated relative to first dose date of risankizumab for subjects switched from Placebo.

**Table 4. Visit Windows for Analysis of Efficacy Variables
 (DLQI/NAPSI/PSSI/PPASI) (RZB_NL Population)**

Window Label	Target Day	Interval
Switch to Risankizumab	1	≤ 1
Week 36S	253	[2, 337]
Week 60S	421	[338, 505]
Week 84S	589	[506, 673]
Week 108S	757	[674, 841]
Week 132S	925	[842, 1009]
Week 156S	1093	[1010, 1177]
Week 180S	1261	[1178, 1303]
Week 192S	1345	[1304, 1429]
Week 216S	1513	[1430, 1597]
Week 240S	1681	[1598, 1765]
Week 264S	1849	[1766, 1933]
Week 288S	2017	[1934, 2087]

S = Switch to Risankizumab

Note: Rx Day calculated relative to first dose date of risankizumab for subjects switched from Placebo.

Table 5. Visit Windows for PASI and sPGA (Relapsed and Retreatment Subjects in Retreatment Population)

Window Label	Target Day	Interval
Entry of Retreatment	1	≤ 1
Week 8R	57	[2, 85]

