Week 16R	113	[86, 155]
Week 28R	197	[156, 239]
Week 40R	281	[240, 323]
Week 52R	365	[324, 407]
Week 64R	449	[408, 491]
Week 76R	533	[492, 575]
Week 88R	617	[576, 659]
Week 100R	701	[660, 743]
Week 112R	785	[744, 827]
Week 124R	869	[828, 911]
Week 136R	953	[912, 995]
Week 148R	1037	[996, 1079]
Week 160R	1121	[1080, 1163]
Week 172R	1205	[1164, 1289]
Week 196R	1373	[1290, 1457]
Week 220R	1541	[1458, 1625]
Week 244R	1709	[1626, 1793]
Week 268R	1877	[1794, 1961]
Week 292R	2045	[1962, 2115]

R = Retreatment of Risankizumab

Note: Rx Day calculated relative to first dose date of retreatment with risankizumab.

Table 6. Visit Windows for PASI and sPGA (OLE Retreated Subjects in Retreatment Population)

Window Label	Target Day	Interval
Entry of OLE	1	≤ 1
Week 12R	85	[2, 127]
Week 24R	169	[128, 211]
Week 36R	253	[212, 295]
Week 48R	337	[296, 379]
Week 60R	421	[380, 463]
Week 72R	505	[464, 547]
Week 84R	589	[548, 631]
Week 96R	673	[632, 715]
Week 108R	757	[716, 799]
Week 120R	841	[800, 883]
Week 132R	925	[884, 967]
Week 144R	1009	[968, 1051]
Week 156R	1093	[1052, 1177]
Week 180R	1261	[1178, 1345]
Week 204R	1429	[1346, 1513]
Week 228R	1597	[1514, 1681]
Week 252R	1765	[1682, 1849]

R = Retreatment of Risankizumab

Note: Rx Day calculated relative to first dose date of retreatment with risankizumab.

Table 7. Visit Windows for DLQI, NAPSI, PSSI, and PPASI (OLE Retreated Subjects in Retreatment Population)

Window Label	Target Day	Interval
Entry of OLE	1	≤ 1
Week 24R	169	[2, 253]
Week 48R	337	[254, 421]
Week 72R	505	[422, 589]
Week 96R	673	[590, 757]
Week 120R	841	[758, 925]
Week 144R	1009	[926, 1093]
Week 156R	1093	[1094, 1177]
Week 180R	1261	[1178, 1345]
Week 204R	1429	[1346, 1513]
Week 228R	1597	[1514, 1681]
Week 252R	1765	[1682, 1849]

R = Retreatment of Risankizumab

Note: Rx Day calculated relative to first dose date of retreatment with risankizumab.

Table 8. Visit Windows for PASI, sPGA, Local Tolerability Assessment, Clinical Laboratory Tests, and Vital Signs (ADA_RZB Population)

Window Label	Target Day	Interval
Switch at Week 16		RxDay_B
Switch to Risankizumab	1	$\leq 1^a$
Week 4S	29	[2, 43]
Week 8S	57	[44, 71]
Week 12S	85	[72, 99]
Week 16S	113	[100, 127]
Week 20S	141	[128, 155]
Week 24S	169	[156, 183]
Week 28S	197	[184, 239]
Week 40S	281	[240, 323]
Week 52S	365	[324, 407]
Week 64S	449	[408, 491]
Week 76S	533	[492, 575]
Week 88S	617	[576, 659]
Week 100S	701	[660, 743]
Week 112S	785	[744, 827]
Week 124S	869	[828, 911]
Week 136S	953	[912, 995]

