Week 148S	1037	[996, 1079]
Week 160S	1121	[1080, 1163]
Week 172S	1205	[1164, 1247]
Week 184S	1289	[1248, 1373]
Week 208S	1457	[1374, 1541]
Week 232S	1625	[1542, 1709]
Week 256S	1793	[1710, 1877]
Week 280S	1961	[1878, 2031]

Table 8. Visit Windows for PASI, sPGA, Local Tolerability Assessment, Clinical Laboratory Tests, and Vital Signs (ADA_RZB Population) (Continued)

Window Label	Target Day	Interval
Switch at OLE		RxDay_OL
Entry of OLE	1	$\leq 1^a$
Week 12S	85	[2, 127]
Week 24S	169	[128, 211]
Week 36S	253	[212, 295]
Week 48S	337	[296, 379]
Week 60S	421	[380, 463]
Week 72S	505	[464, 547]
Week 84S	589	[548, 631]
Week 96S	673	[632, 715]
Week 108S	757	[716, 799]
Week 120S	841	[800, 883]
Week 132S	925	[884, 967]
Week 144S	1009	[968, 1051]
Week 156S	1093	[1052, 1177]
Week 180S	1261	[1178, 1345]
Week 204S	1429	[1346, 1513]
Week 228S	1597	[1514, 1681]
Week 252S	1765	[1682, 1835]

S = Switch to Risankizumab

a. If time is collected in vital signs, restrict to records prior to the first dose after switch to RZB.

Note: RxDay_B calculated relative to the first dose date in Part B.

RxDay_OL calculated relative to the first dose date of OLE.

Table 9. Visit Windows for NAPSI, PPASI, PSSI, and DLQI (ADA_RZB Population)

Window Label	Target Day	Interval
Switch at Week 16		RxDay_B
Switch to Risankizumab	1	≤ 1
Week 28S	197	[2, 281]
Week 52S	365	[282, 449]
Week 76S	533	[450, 617]
Week 100S	701	[618, 785]
Week 124S	869	[786, 953]
Week 148S	1037	[954, 1121]
Week 172S	1205	[1122, 1247]
Week 184S	1289	[1248, 1373]
Week 208S	1457	[1374, 1541]
Week 232S	1625	[1542, 1709]
Week 256S	1793	[1710, 1877]
Week 280S	1961	[1878, 2031]
Switch at OLE		RxDay_OL
Entry of OLE	1	≤ 1
Week 24S	169	[2, 253]
Week 48S	337	[254, 421]
Week 72S	505	[422, 589]
Week 96S	673	[590, 757]
Week 120S	841	[758, 925]
Week 144S	1009	[926, 1051]
Week 156S	1093	[1052, 1177]
Week 180S	1261	[1178, 1345]
Week 204S	1429	[1346, 1513]
Week 228S	1597	[1514, 1681]
Week 252S	1765	[1682, 1835]

S = Switch to Risankizumab

Note: RxDay_B calculated relative to the first dose date in Part B.

RxDay_OL calculated relative to the first dose date of OLE.

Table 10. Visit Windows for Analysis of PASI, sPGA, Local Tolerability Assessment, Clinical Laboratory Tests, and Vital Signs (UST_RZB, FUM_RZB, RZB_Japan Populations)

Window Label	Target Day	Interval
Entry of Study M15-997	1	≤ 1 ^a
Week 12	85	[2, 127]
Week 24	169	[128, 211]
Week 36	253	[212, 295]
Week 48	337	[296, 379]
Week 60	421	[380, 463]
Week 72	505	[464, 547]

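### SAP Table 2 fits OLE entry at Week 52; if 1311.30 subjects enter at Week 44, as Tables 8-9 imply, prompt entrants lose one scheduled DLQI/NAPSI/PPASI/PSSI assessment and have no observed Week 208 value

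*SAP*

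**What the plan says.** SAP Section 5.1 pools the risankizumab arms of five studies: "The RZB population consists of subjects who were randomized to risankizumab 150 mg in Studies 1311.3, 1311.30, 1311.28, 1311.38, and M16-178". Section 6.0 gives this population one set of windows, counted from the first risankizumab dose. Table 1 covers PASI, sPGA, local tolerability, laboratory tests and vital signs. Table 2 covers DLQI, NAPSI, PSSI and PPASI. In both tables Week 208 is Days 1416-1541 and Week 232 is Days 1542-1709. Week 196 is Days 1332-1415 in Table 1 and Days 1290-1415 in Table 2. Boundaries lie midway between nominal days, and when two assessments share a window only the one nearer the target day is used.

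Tables 8 and 9 give separate windows for the 1311.30 subjects who were randomized to adalimumab and switched to risankizumab.

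Section 10.1 makes LOCF primary and OC the sensitivity analysis; OC leaves out a subject with no evaluation at the visit. Section 10.5 adds that "PASI 90 and sPGA clear or almost clear will be summarized among the RZB Population at Week 208 and Week 256", by antibody status up to each of those weeks. The Protocol synopsis has antibody blood taken "just prior to dosing at Baseline, Week 48, Week 96, Week 156, Week 204 and End of Treatment (EOT) visit".

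On entry timing, SAP Section 4.2 says "The subject preferably has the Baseline visit of Study M15-997 on the same day of the completion visit of the preceding study", with a delay of up to 8 weeks allowed.

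**The concern.** The SAP appears to work with two different OLE entry weeks. Tables 1 and 2 assume Week 52 for everyone in the RZB Population, while Tables 8 and 9 imply Week 44 for Study 1311.30, whose risankizumab arm belongs to the RZB Population.

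If that arm also finishes at Week 44, its OLE visits come 8 weeks earlier than Tables 1 and 2 expect. The pinch is around OLE Week 156, where visits change from 12-weekly to 24-weekly. In Table 2 two scheduled assessments then compete for one window and the next window is empty. A value collected on schedule is discarded, and the subject drops out of the Week 208 OC summary because of window placement, not missing data. A difference between LOCF and OC at Week 208 would then partly reflect a change in study mix and could be mistaken for an effect of dropout.

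The antibody summary has a related oddity. The OLE Week 156 blood sample can count towards status by Week 208, while PASI and sPGA from the same visit are labelled Week 196.

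**Working it through.** **1. Reproduce the SAP windows.** Nominal day = 7 × week + 1, so Weeks 172, 196, 208 and 232 are Days 1205, 1373, 1457 and 1625. Midpoints: (1205 + 1373)/2 = 1289; (1373 + 1457)/2 = 1415; (1457 + 1625)/2 = 1541. This gives Week 196 = 1290-1415 in Table 2 and Week 208 = 1416-1541 in both tables, as printed.

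**2. Entry week implied by each table.** After Week 156, OLE efficacy visits are at Weeks 180, 204, 228 and 252 (Protocol Appendix C).
- Tables 1 and 2: 208 − 156 = 304 − 252 = 52.
- Table 8, switch at Week 16: 184 − 156 = 280 − 252 = 28 weeks after the switch. Table 9 agrees (172 − 144 = 28). Entry is then Week 16 + 28 = 44, Day 309.
- The Section 10.5 weeks match the antibody draws on a Week 52 entry: 156 + 52 = 208 and 204 + 52 = 256.

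**3. Map a same-day, on-schedule Week 44 entrant** (Day = 309 + 7 × OLE week).

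| OLE week | Actual week | Day | Table 1 label | Table 2 label (shift) |
|---|---|---|---|---|
| 144 | 188 | 1317 | 184 | 196 (+8) |
| 156 | 200 | 1401 | 196 | 196 (−4) |
| 180 | 224 | 1569 | 232 | 232 (+8) |
| 204 | 248 | 1737 | 256 | 256 (+8) |

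In Table 2, every on-schedule OLE visit except Week 156 carries a +8-week shift. In Table 1 the shift is −4 weeks up to OLE Week 156 and +8 afterwards. No visits collide there, but Week 208 is skipped.

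**4. Which value is discarded.** Against the Week 196 target, Day 1373, OLE Week 144 is 1373 − 1317 = 56 days away and OLE Week 156 is 1401 − 1373 = 28 days away. The OLE Week 144 assessment goes unused.

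**5. Allow for timing.** Let the 1311.30 completion visit vary by f = −7 to +7 days (an assumption; its tolerance is not given), the entry gap be g days, and each OLE visit vary by v = −7 to +7 days (Protocol Section 5.1). OLE Week 156 falls on Day 1401 + f + g + v and reaches Week 208 only if f + g + v ≥ 15.
- g = 0: the largest sum is 14, so 0 of 15 × 15 = 225.
- g = 0 to 7: 0 + 1 + 3 + 6 + 10 + 15 + 21 + 28 = 84 of 15 × 8 × 15 = 1,800 (4.7%). With completion exactly on Day 309, 0 of 120.
- g = 8 to 28: from 36 to 224 of 225. g = 29 to 56: always.
- OLE Week 180 lies on Days 1555-1639 over all gaps of 0-56 days and never falls in Week 208.
- Table 2, g = 0 to 7: OLE Week 144 lies on Days 1303-1338, always in Week 196. Both visits are in Week 196 in (1,800 − 84) × 15 = 25,740 of 27,000 (95.3%).

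**6. Test a Week 208 start at Day 1388 in Table 2.** Over all gaps of 0-56 days, OLE Week 144 comes no later than 1317 + 7 + 56 + 7 = 1387, so it always stays in Week 196. OLE Week 156 comes no earlier than 1401 − 14 = 1387 and misses Week 208 in 1 of 15 × 57 × 15 = 12,825 combinations. For g = 0 to 7 the two visits are separated in (1,800 − 1) × 15 = 26,985 of 27,000.

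**The case against.** The documents nowhere state the length of 1311.30, and Week 44 is read off windows written for another arm. That stands: confirmation has to come first.

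An empty Week 208 can also be called correct windowing. A Week 200 value is 4 weeks from Week 196 and 8 from Week 208, the even-split rule picks the nearer label, and OC reports truthfully that nobody was assessed near Week 208. For Table 1 this prevails. A reader might infer that Table 1 needs the same boundary change. The documents do not support that: OLE Weeks 144, 156 and 180 are three visits facing four labels (184, 196, 208, 232), so one label must be empty. Moving the boundary would only shift the gap to Week 196 and would replace the OLE Week 156 value there with the older OLE Week 144 value under LOCF.

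For Table 2 the argument is weaker. There a scheduled assessment is discarded, and OLE Week 156 is the one visit out of step with the rest.

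The path-specific windows in Tables 5-6 and 8 show that the SAP accepts such windows within one population. They keep midpoint boundaries, however, so they are no precedent for an off-midpoint one.

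Finally, the counts above are equally weighted combinations, not probabilities, and pandemic rescheduling could move real visits. Both remarks are fair.

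**Conclusion.** The point holds for Table 2, on condition that the 1311.30 risankizumab arm completes at Week 44. For entrants within about a week, the OLE Week 144 and 156 assessments of DLQI, NAPSI, PPASI and PSSI nearly always share the Week 196 window. One is discarded and Week 208 has no OC value. Entrants delayed by 29 days or more are not affected.

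For PASI and sPGA in Table 1 there is a Week 208 OC gap that needs a footnote, plus a mismatch in the OC version of the Section 10.5 summary.

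A reader might infer that Week 208 efficacy, or the antibody summary as a whole, is unreliable. The documents do not support that. Under primary LOCF the OLE Week 156 value is carried to Week 208, the same visit that supplies the antibody sample. OLE Week 204 always falls in Week 256 (Days 1723-1807). No statistical test is planned.

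Neither the share of 1311.30 in the RZB Population nor the spread of entry delays is given, so the effect on any OC percentage cannot be computed. This is a minor point.

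**What to change.** Confirm the completion week of the 1311.30 risankizumab arm. If it is Week 44:

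- **Table 2, 1311.30 subjects only:** end Week 196 at Day 1387 and start Week 208 at Day 1388.
- **Table 1:** leave the windows as they are. Add a footnote that Week 208 OC omits most prompt 1311.30 entrants.
- **Section 10.5, OC version:** for these subjects use the OLE Week 156 PASI and sPGA (actual Week 200) as the Week 208 value, and say so. This denominator will then differ from the by-visit Week 208 OC table.

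The cost is two rows of one table, one condition in the window program, a footnote and a sentence; no new data are needed. The downsides should be accepted openly. The boundary departs from the even-split rule for one study. The Day 1401 value lies 1457 − 1401 = 56 days from its target instead of 28. Week 196 in Table 2 then uses the OLE Week 144 value for these subjects, as it already does for Week 52 entrants.
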